5.6 Subgroup Analysis

Subgroup analysis will be performed. The following variables will define subgroups.

⁴ Vincent JL, Moreno R, Takala J, et al: The SOFA (Sepsis-related Organ Failure Assessment) score to describe organ dysfunction failure: On behalf of the Working Group on Sepsis-Related Problems of the European Society of Intensive Care Medicine. *Intensive Care Med* 1996; 22:707–710.

⁵ Vincent JL, Angus DC, Artigas A, Kalis A, Basson BR, Jamal HH, Johnson III G., Bernard GR for the PROWESS Study Group. Effects of drotrecogin alfa (activated) on organ dysfunction in the PROWESS trial. *Crit Care Med* 2003; 31:834 – 840.

- Stage 2 and Stage 3 AKI
- Acuity of AKI (i.e., whether or not AKI is diagnosed at time of presentation of abdominal infection or surgically confirmed NSTI, or during the 48 hours from the suspected diagnosis of abdominal infection or surgical confirmation of NSTI; developed AKI up to <24 hours or 25 to 48 hours after the suspected diagnosis of abdominal infection or surgical confirmation of NSTI)
- AKI diagnosed via creatinine criteria vs. urine output criteria
- Abdominal infection or NSTI
- Age ≥ 18 to ≤ 75 and > 75 to ≤ 85 years old
- Baseline APACHE II ≥ 10 and < 10
- Cardiovascular failure yes and no
- Respiratory failure yes and no
- Gender male and female
- Causcasian and other
- BMI category (< 30 , 30-40, > 40)
- Day 14 mSOFA ≤ 1 and Day 14 mSOFA ≥ 2

The following tables will be provided for each subgroup. Results for the primary endpoint will be summarized in a forest plot.

14.2.1.1	Numbers and Percentages of Subjects Achieving Freedom from Durable Loss of Renal Function and Improvement in Durable Loss of Renal Function at Day 28 Using LOCF ITT Analysis Set
14.2.2.1	Numbers and Percentages of Subjects Achieving Secondary Freedom from or Improvement in Durable Loss of Renal Function Endpoints at Days 14, 28, and 90 ITT Analysis Set

5.7 Analysis of Other Covariate Effects

Covariates will be assessed for potential confounding (due to lack of perfect randomization balance) or effect modification (subgroup efficacy heterogeneity) using Mantel-Haenszel stratified analyses and/or multiple logistic regression. Covariates will include the set of variables listed above for subgroup analyses. Other baseline variables in which randomization failed to produce balance between groups will be examined in supporting analyses. Covariate effects on estimates and interactions will be assessed to see if there is evidence of efficacy heterogeneity. Results from all subgroups analyses will be considered hypothesis-generating.

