7. INVESTIGATIONAL PLAN

7.1 Dose Selection Rationale

The formulation in the two completed clinical studies (ATB-001, ATB-201) and the ongoing clinical study with Reltecimod (ATB-202) is identical to the formulation used in this clinical study in patients with SA-AKI (ATB-203). Reltecimod will be dosed according to the patient's actual body weight, at 0.50 mg/kg, and will be administered as an intravenous infusion over 10 minutes.

The rationale for the proposed dose in the planned SA-AKI study is based on data from the Phase 2 study in NSTI. In this study with two Reltecimod dose groups (0.25 and 0.50 mg/kg), evidence for a dose response was seen across multiple domains of efficacy variables. A linear dose response emerged for individual endpoints such as: SOFA score (measured either as total score at Day 14, individual organ score at Day 14, change in total score between days 1-14, percent of patients with organ failure at Day 14, SOFA score over time in patients presenting with organ failure at Day 1), debridements (measured as number of debridements to Day 7 or 28, percent of patients needing only one debridement, percent of patients needing less than 4 debridement to resolve the infection), and response of inflammatory biomarkers (measured systemically in plasma and at the tissue level from the site of infection).

Overall, these results suggest that the 0.50 mg/kg dose is superior to the 0.25 mg/kg dose regarding efficacy in NSTI patients. The safety profile was similar for the two Reltecimod doses. Thus, the 0.50 mg/kg dose was chosen for further clinical studies. This dose was shown to be efficacious in the post-hoc analysis of NSTI patients with AKI. The 0.50 mg/kg dose provided the highest treatment benefit in these patients, as judged by the rate of complete recovery from AKI. Thus, it was chosen for further studies in patients with SA-AKI.

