3.7.1 SOFA Score Definition

Screening SOFA score: includes measurements of six organ systems (cardiovascular, respiratory, renal, coagulation, GI/hepatic, and CNS) with data values evaluated any time after arrival at study site hospital. *Follow-up SOFA scores:* measurements of (the same) six organ systems with data values measured on Days 1, 3, 7, and 14, and calculated retrospectively.

Where it is not possible to take arterial blood gases to determine the SOFA respiratory parameter, SpO₂ value can be converted to a PaO₂ value to allow calculation of the PaO₂/FiO₂ ratio.

For this study, the liver component is excluded in the primary total sum score, and the resulting sum score is referred to in this study as 'mSOFA'.

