4.2 Secondary Effectiveness Endpoints

The secondary effectiveness endpoints for this study are:

- Freedom from durable loss of renal function at Day 14
- Freedom from durable loss of renal function at Day 90

Reference creatinine values, baseline AKI stage and percentage loss of eGFR at Days 14 and 90 will be determined through algorithmic determination (see details above). Percentage loss of eGFR determined algorithmically will be based on a comparison of eGFR at screening compared to an algorithmically determined reference creatinine value

- Resolution of organ dysfunction (organ resolution is defined as having a total mSOFA score of ≤ 1) at Day 14
- Resolution of specific organ dysfunction (defined as having an individual organ mSOFA score of ≤ 1) at Day 14
- Critical care and hospital stay parameters
 - Hospital length of stay
 - ICU length of stay
 - ICU-free days in 28 days
 - Days on ventilator
 - Ventilator free days in 28 days
 - Vasopressor days
 - Vasopressor free days in 28 days
 - Discharge status

- Patient survival at Days 14, 28 and 90.
- Presentation of Stages 1, 2, or 3 AKI (using the KDIGO criteria)
- **Stratifications involving Day 14 mSOFA \leq 1 vs Day 14 mSOFA \geq 2**
 - Compare critical care between Day 14 mSOFA \leq 1 vs Day 14 mSOFA \geq 2
 - Compare dose groups in those with Day 14 mSOFA \leq 1
 - Compare dose groups in those with Day 14 mSOFA \geq 2
- Among patients presenting with cardiovascular failure (shock), dose group predicting Day 14 mSOFA \leq 1
- Survival to Day 90 as a function of *freedom from durable loss of renal function at 28* (overall and by dose group)

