8.8 Subgroup Analysis

As noted in Section 5.6, the following variables will define subgroups.

- Stage 2 and Stage 3 AKI
- Acuity of AKI (i.e., whether or not AKI is diagnosed at time of presentation of abdominal infection or surgically confirmed NSTI, or during the 48 hours from the suspected diagnosis of abdominal infection or surgical confirmation of NSTI; developed AKI up to <24 hours or 25 to 48 hours after the suspected diagnosis of abdominal infection or surgical confirmation of NSTI)
- AKI diagnosed via creatinine criteria vs. urine output criteria
- Abdominal infection or NSTI
- Age ≥ 18 to ≤ 75 and >75 to ≤ 85 years old
- Baseline APACHE II ≥ 10 and < 10
- Cardiovascular failure yes and no
- Respiratory failure yes and no
- Gender male and female
- Caucasian and other
- BMI category (<30 , $30-40$, >40)
- Day 14 mSOFA ≤ 1 and Day 14 mSOFA ≥ 2
- Selected baseline pathogen type

The following tables will be provided for each subgroup. Results for the primary endpoint will be summarized in a forest plot.

14.2.1.1	Numbers and Percentages of Subjects Achieving Freedom from Durable Loss of Renal Function and Improvement in Durable Loss of Renal Function at Day 28 Using LOCF
----------	--

	ITT Analysis Set
14.2.2.1	Numbers and Percentages of Subjects Achieving Secondary Freedom from or Improvement in Durable Loss of Renal Function Endpoints at Days 14, 28, and 90 ITT Analysis Set

9 Presentation of Safety Evaluations

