15.3 SOFA – Sequential Organ Failure Assessment Score

The following is provided in the Clinical Trial Protocol and is repeated here for convenience.

Can range from 0-24.

Value	0	1	2	3	4
Respiratory PaO₂/FiO₂¹	>400	≤400	≤300	≤200 with respiratory support	≤100 with respiratory support
Coagulation Platelets	>150	≤150	≤100	≤50	≤20
GI Total Bilirubin	<1.2	1.2-1.9	2.0-5.9	6.0-11.9	≥12.0
Cardiovascular²	No hypo- tension	MAP <70	Dopa ≤5 PE <100	Dopa > 5 Epi ≤ 0.1 NE ≤ 0.1 PE 100- 300	Dopa>15 Epi>0.1 NE>0.1 PE>300 VP>0.01
Neurology GCS	15	13-14	10-12	6-9	<6
Serum Creatinine OR Urine Output	<1.2	1.2-1.9	2.0-3.4	3.5-4.9 <500cc/ day	≥5.0 <200cc/ day

1. For patients on supplemental oxygen via nasal cannula, nasopharyngeal catheter or mask and for converting SpO₂ values to PaO₂ use the attached oxygen conversion tables.

2. Doses of dopamine (Dopa), epinephrine (Epi), norepinephrine (NE) are in micrograms/kg/min; phenylephrine (PE) is micrograms/min; vasopressin (VP) is U/min. Vasopressors must have been administered for at least one hour.

16 Appendix 7: Prior and Concomitant Medications

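### SAP 5.7 uses Day 14 mSOFA, a post-dose efficacy endpoint, as a covariate for randomisation imbalance, and SAP 5.6 and 8.8 use it as an efficacy subgroup; only supportive analyses are affected

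*SAP*

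**What the plan says.** SAP 5.7 names two aims for its covariate work, confounding from chance imbalance and effect modification. It names two methods, Mantel-Haenszel stratification and logistic regression. The covariate set is defined by reference: "Covariates will include the set of variables listed above for subgroup analyses". No variable is exempted.

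The list referred to is in SAP 5.6. Its last entry is Day 14 mSOFA, split at ≤ 1 and ≥ 2. Every listed subgroup receives the primary-endpoint table (14.2.1.1) and the table titled "Numbers and Percentages of Subjects Achieving Secondary Freedom from or Improvement in Durable Loss of Renal Function Endpoints at Days 14, 28, and 90" (14.2.2.1). In addition, "Results for the primary endpoint will be summarized in a forest plot". SAP 8.8 repeats the list ("As noted in Section 5.6, the following variables will define subgroups"), again with Day 14 mSOFA.

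Other sections show what this variable is:
- SAP 4.2 makes it a secondary endpoint: "organ resolution is defined as having a total mSOFA score of" 1 or less at Day 14. The same section plans comparisons of dose groups within each Day 14 mSOFA level.
- SAP 3.7.1 defines the modification: "For this study, the liver component is excluded in the primary total sum score". The other five items stay, including the one labelled "Serum Creatinine OR Urine Output" in SAP 15.3.
- SAP 5.11.3 says carry-forward is needed so that each patient has a Day 14 value, then rules it out after death.

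**The concern.** Day 1 begins with the infusion (protocol 7.3, Visit 2), so a Day 14 score is an outcome. A difference between arms in that score may be the drug working, and it says nothing about whether randomisation balanced the groups.

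The sponsor has reason to expect the drug to move it. Of the Phase 2 study in necrotizing soft tissue infection, protocol 7.1 says: "A linear dose response emerged for individual endpoints such as: SOFA score (measured either as total score at Day 14". That concerns total SOFA in another population, so it makes an effect on Day 14 mSOFA plausible without establishing one.

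Adjusting for, or stratifying by, a variable that treatment changes no longer compares the randomised groups. Part of the effect may be adjusted away, or patients with different prognosis may be compared. Two rows of the forest plot, the matching subgroup tables and any adjusted or interaction result under 5.7 could then be misread as efficacy heterogeneity or as the correction of a chance imbalance.

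**Working it through.** **1. The plan's own figures.** With 60 per arm and success rates of 50% and 75%, the unadjusted test has power 0.8897 at one-sided 0.05 (SAP 2.1.2 states 89%) and 0.8157 at one-sided 0.025 (protocol 12.5.2 states 81.6%). Neither calculation uses a covariate, so neither changes if Day 14 mSOFA is removed.

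**2. Overlap with the outcome.** In SAP 15.3 a creatinine of 2.0–3.4 mg/dL scores 2, so a Day 14 creatinine of 2.0 or more by itself puts a patient in the ≥ 2 level. SAP 3.10.4 computes the Day 14 renal endpoint from Day 14 creatinine, and protocol 7.3 (Visit 7) lets the same laboratory draw supply the SOFA value. Table 14.2.2.1 would therefore report that endpoint within levels partly defined by the same measurement. The overlap is not universal: Visit 7 has SOFA parameters taken on the day of discharge for patients who leave earlier.

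**3. Illustration of effect removed.** The documents give no association between Day 14 mSOFA and the Day 28 endpoint, so the inputs below are assumed. Let
- p = P(mSOFA ≤ 1) on placebo, and p + S on drug;
- b = placebo success in the ≥ 2 level, and b + L in the ≤ 1 level;
- D = drug-minus-placebo difference within a level, equal in both levels, with no shared prognosis linking the score and the endpoint.

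Placebo success is b + L × p. Drug success is b + D + L × (p + S). The overall difference is D + L × S. Setting it to the planned 0.25 gives D = 0.25 − L × S.

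With L = 0.3:
- S = 0.10: D = 0.25 − 0.03 = 0.22.
- S = 0.25: D = 0.25 − 0.075 = 0.175.

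Check of the second case with p = 0.40. Placebo levels are 0.38 and 0.68, and 0.60 × 0.38 + 0.40 × 0.68 = 0.50. Drug levels are 0.555 and 0.855, and 0.35 × 0.555 + 0.65 × 0.855 = 0.75.

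The extreme case is an effect that runs wholly through the score, so that L × S = 0.25 and D = 0. An example is 90% success at ≤ 1 and 20% at ≥ 2, with P(mSOFA ≤ 1) rising from 0.429 to 0.786 (0.7 × 0.357 = 0.25). Across three such settings, simulated with 60 per arm at one-sided 0.05, a Mantel-Haenszel test stratified on the score rejected in 5.3% to 5.6% of trials. The crude test rejected in 89% to 90%.

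**4. Illustration of selection.** Assume no drug effect on the Day 28 endpoint, an unmeasured prognosis shared by the score and the endpoint (log-odds 1.5 per SD), and a drug that raises P(mSOFA ≤ 1) from 50% to 70%. In simulation the crude difference was about 0, but the difference was about −0.06 in each level and the Mantel-Haenszel odds ratio was 0.77. With no drug effect on the score, the level differences returned to 0 and the odds ratio to 1.00. Early deaths were not modelled here.

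**5. Early deaths.** A patient who dies before Day 14 fails the primary endpoint, which requires being alive at Day 28. SAP 5.11.3 does not say whether that patient belongs to ≤ 1, to ≥ 2, or to neither, so the denominators of the two forest-plot rows are undefined.

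**The case against.** The best defence is that little depends on this. SAP 5.7 calls all subgroup results hypothesis-generating, SAP 5.3 and 5.9 describe secondary analyses as generally descriptive, and Appendix 1 lists no adjusted efficacy table. SAP 4.2 deliberately plans comparisons within Day 14 mSOFA levels, so the sponsor evidently wants that display. SAP 5.7 also covers effect modification, and its next sentence speaks of other baseline variables, which suggests that the inclusion is a careless cross-reference.

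Most of this stands, and it keeps the point minor. It does not cure the text. A careless cross-reference still tells the programmer to use the variable. A level that treatment may change does not define a subgroup at randomisation, so a difference across its levels is not evidence of effect modification. The wish for a descriptive display is met by keeping the 4.2 comparisons with a label.

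A reader might also infer that the SAP contradicts the protocol here. Protocol 12.7 does not list this subgroup, and 12.9 names severity scores at baseline, but neither list is closed. The SAP therefore adds to the protocol, and the objection has to rest on the timing of the variable.

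**Conclusion.** The concern holds as a minor point. A post-dose secondary endpoint is used as a covariate for randomisation imbalance and as an efficacy subgroup, and following the text can distort those supportive comparisons. The primary chi-square test is unadjusted and unaffected, as are alpha, N = 120 and power.

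The size and direction of any distortion are unknown. The 0.22 and 0.175 rest on assumed values of L and S, an equal direct effect in both levels, and no shared prognosis.

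Three stronger readings are tempting but unsupported:
- *The within-level difference must lie between 0 and 0.25.* That follows only from the model in step 3. Step 4 shows that shared prognosis can push the difference below zero.
- *A high Day 14 creatinine both fixes the mSOFA level and fails the Day 14 endpoint.* This depends on the comparator. SAP 4.1 measures loss from reference eGFR, while the formula in 3.10.4 uses screening eGFR. Take reference 1.0, screening 2.5 and Day 14 2.2 mg/dL. Against reference, eGFR falls by 1 − 2.2^(−1.154) = 60% and the patient fails. Against screening it rises by 0.88^(−1.154) − 1 = 16% and the patient passes. Shared use of creatinine is established; a fixed outcome is not.
- *Early deaths are excluded, and Phase 2 deaths show by how much this matters.* SAP 5.11.3 leaves their placement unspecified, and protocol 4.1.3.3.2 gives no day of death, so those deaths cannot be counted as occurring before Day 14.

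**What to change.** 1. Delete Day 14 mSOFA from the subgroup lists in SAP 5.6 and 8.8.
2. In SAP 5.7, restrict covariates to variables measured before dosing. If organ severity is wanted, use screening mSOFA, whose components are already collected.
3. If the dose-group comparisons within Day 14 mSOFA levels in SAP 4.2 are kept, state that they are descriptive and do not estimate a treatment effect, and say where deaths before Day 14 are placed (one sentence in 4.2 or 5.11.3). Displays by mSOFA level that pool the arms, such as Table 14.2.5.5, can stay.

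The cost is SAP wording and two fewer rows in the forest plot. No new data are needed, and the primary test, sample size and interim rules do not change. SAP 1 says the document is finalised before unblinding, so the edit belongs before then.

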5.8 Multiplicity

There is a single primary hypothesis test utilizing a clinical success endpoint, freedom from durable loss of renal function at Day 28. Therefore, there is no issue with regard to multiplicity .

5.9 Descriptive Analyses of Secondary Endpoints

Secondary endpoints have been specified from several domains including critical care and hospital stay parameters (ICU days and ICU-free days, ventilator days and –free days, vasopressor days and –free days, hospital LOS, and clinical systemic parameters (SOFA over time, incidence and recovery from AKI). Analyses for these endpoints will generally be descriptive, with emphasis on characterizing clinical effect sizes⁶. Nominal p-values will be presented as an aid to interpretation. Categorical outcomes will be summarized using counts and percentages with nominal p-values determined through chi-square or exact methods. Critical care and hospital stay endpoints will be described using non-parametric approaches including using concordance statistics (c-stat) to characterize clinical effect size and Wilcoxon rank sum tests to determine nominal statistical significance. Methods appropriate for time-to-event endpoints including survival and life-table methods will be used for time-to-event endpoints.

5.10 Analysis of Event-time and Overall Survival

Time-to-event endpoints will be assessed in descriptive analyses using survival and life table methods as appropriate and illustrated using Kaplan-Meier survival curves⁷. The significance of group will be assessed using logrank statistics.

5.11 Handling of Missing Data

5.11.1 Intent-to-Treat

The purpose of intent-to-treat comparisons is to ensure that randomization is protected (i.e., all groups have comparable baseline characteristics and that any differences besides therapy are due to chance) and to preclude the possibility of bias due to selectively excluding subjects from therapy groups. This is intended to avoid systematic differences among the groups attributable to factors other than therapy assignment⁸. Therefore, we will attempt to include all randomized patients, regardless of intervention or length of follow-up in the primary efficacy comparison.

5.11.2 LOCF of Day 28 and Day 90 Creatinine

In order to determine the primary endpoint, freedom from durable loss of eGFR at Day 28, creatinine is necessary. Patients surviving to Day 28 or later but with missing Day 28 creatinine will have their Day 28 creatinine values determined through LOCF. The same procedure will be used for Day 90 Creatinine.

5.11.3 mSOFA Scores

mSOFA scores over time will be assessed as 1) observed cases, and 2) LOCF.

⁶ Cohen, J. (1988). *Statistical power analysis for the behavioral sciences* (2nd ed.). New York, Academic Press.

⁷ Kaplan EL and Meier P. Nonparametric estimation from incomplete observations, *Journal of the American Statistical Association*, **53**:457-481, 1959

⁸ Knickerbocker R. Intent-to-Treat Analyses. In: Chow S-C, ed. *Encyclopedia of Biopharmaceutical Statistics*. Marcel Dekker; 2000.

Individually missing mSOFA component values due to non-measurement are conventionally assumed as normal and this convention will be followed for this study.

LOCF will not be applied to missing mSOFA scores after patient death in analyses that employ LOCF to describe mean values of time. Therefore, analysis of mSOFA mean values using LOCF will focus on morbidity rather than mortality. Also, LOCF will not be used for missing mSOFA after Day 14.

In categorical analyses including formulation of the secondary effectiveness endpoint, total mSOFA score at Day 14 ≤ 1 , LOCF is necessary to guarantee that every patient has a value at Day 14. LOCF will not be performed after patient death.

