3.10.3 Day 28 eGFR

Day 28 eGFR will be determined by converting Day 28 creatinine to Day 28 eGFR using the following formula:

$$\text{Day 28 eGFR (mL/min/1.73 m}^2\text{)} = 175 \times (\text{Cr Day 28})^{-1.154} \times (\text{Age})^{-0.203} \times (0.742 \text{ if female}) \times (1.212 \text{ if African American}).$$

Percentage loss in eGFR at Day 28 will be determined using the following formula.

$$\text{Percentage loss in eGFR at Day 28} = 100\% \text{ times } [\text{Screening eGFR} - (\text{Day 28 eGFR}) / \text{Screening eGFR}]. \text{ If percentage loss } \geq 37\% \text{ then patient fails key secondary endpoint.}$$

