3.10.4 Day 14 eGFR

Day 14 eGFR will be determined by converting Day 14 creatinine to Day 14 eGFR using the following formula:

$$\text{Day 14 eGFR (mL/min/1.73 m}^2\text{)} = 175 \times (\text{Cr Day 14})^{-1.154} \times (\text{Age})^{-0.203} \times (0.742 \text{ if female}) \times (1.212 \text{ if African American}).$$

Percentage loss in eGFR at Day 14 will be determined using the following formula.

Percentage loss in eGFR at Day 14 = 100% times [Screening eGFR - (Day 14 eGFR) / Screening eGFR]. If percentage loss $\geq 37\%$ then patient fails the Day 14 endpoint.

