3.10.5 Day 90 eGFR

Day 90 eGFR will be determined by converting Day 90 creatinine to Day 90 eGFR using the following formula:

Day 90 eGFR (mL/min/1.73 m²) = $175 \times (\text{Cr Day 14})^{-1.154} \times (\text{Age})^{-0.203} \times (0.742 \text{ if female}) \times (1.212 \text{ if African American})$.

Percentage loss in eGFR at Day 90 will be determined using the following formula:

Percentage loss in eGFR at Day 90 = 100% times [Screening eGFR - (Day 90 eGFR) / Screening eGFR]. If percentage loss $\geq 37\%$ then patient fails the Day 90 endpoint.

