3.10.6 Additional Processing Details

Based on experience gained through processing of AKI endpoints in the recently completed ATB-202 study, the following data processing convention will be employed.

- To account for renal replacement therapy (RRT), the exact dates on which the patient is on dialysis will be determined and compared to the exact date on which the labs were drawn for the creatinine sample. If the sample was drawn within 2 days from RRT start then it was excluded from all analyses.
- If the reference creatinine is greater than 1.4, then all available creatinine values obtained on Day 10 and after, including unscheduled visits, will be evaluated. If the maximum is 1.5x the minimum, then the reference creatinine is replaced by the MDRD.
- LOCF will be used for missing Day 14 creatinine starting from Day 10.
- LOCF will be used for missing Day 28 creatinine starting from Day 7.

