8.3 Secondary and Exploratory AKI Recovery Endpoints

Table 14.2.2.1 summarizes treatment group comparisons based on secondary AKI recovery endpoints in the mITT analysis set including:

- Freedom from durable loss of renal function at Day 14
- Freedom from durable loss of renal function at Day 90
- Improvement or freedom from durable loss at Day 14
- Improvement or freedom from durable loss at Day 28
- Improvement or freedom from durable loss at Day 90

Tables 14.2.2.2 and 14.2.2.3 repeat these comparisons in the AT and PP analysis sets, respectively.

8.4 mSOFA Scores

Table 14.2.4.1 summarizes observed modified total score, organ specific scores, and mSOFA total scores at Screening, Day 1, Day 3, Day 7, and Day 14.

Table 14.2.4.2 provides the same summary after application of last-value-carried forward (LOCF). LOCF was not applied after patient death.

Table 14.2.4.3 summarizes mSOFA at Screening and changes from Screening to Day 1, Day 7, and Day 14 for observed cases.

Table 14.2.4.4 provides the same summary after application of LOCF.

Table 14.2.4.5 summarizes the percentages of subjects with resolution of organ dysfunction (organ resolution is defined as having a total mSOFA score of ≤ 1) at day 14 and the resolution of specific organ dysfunction defined as having an individual organ SOFA score of ≤ 1 at Day 14.

8.5 Critical Care and Hospital Stay Parameters, to be Measured until Day 28

The following critical care and hospital stay parameters will be assessed.

- Hospital length of stay (days)
- ICU free days
- Days in ICU
- Days on ventilator
- Ventilator free days
- Vasopressors days
- Vasopressors free days
- Discharge status

Because of the expected skewness in the distributions of these parameters, non-parametric Wilcoxon rank sum tests will be used to assess the nominal statistical significance of treatment group differences in these parameters. Table 14.2.5.1 will provide summary statistics by treatment groups including N, mean, median, standard deviation, and minimum, and maximum values.

Table 14.2.5.2 summarizes hospital discharge status.

Table 14.2.5.3 summarizes hospital readmissions.

Table 14.2.5.4 will summarize critical care and hospital stay parameters over days 1 to 28 comparing by primary effectiveness status (success versus failure).

Table 14.2.5.5 will summarize critical care and hospital stay parameters over days 1 to 28 comparing subjects with Day 14 mSOFA ≤ 1 versus Day 14 mSOFA ≥ 2 .

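### SAP 3.10.5 says Day 90 eGFR comes from the Day 90 creatinine, but the formula beneath uses the Day 14 creatinine

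*SAP*

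**What the plan says.** SAP 3.10.5 opens: "Day 90 eGFR will be determined by converting Day 90 creatinine to Day 90 eGFR using the following formula". The formula directly beneath is 175 × (Cr Day 14)^−1.154 × Age^−0.203, with the usual sex and race factors. The section then computes the percentage loss from the quantity labelled Day 90 eGFR, and at a loss of 37% or more "then patient fails the Day 90 endpoint".

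Three other parts of the SAP bear on this:

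- **5.11.2** sets LOCF for a missing Day 28 creatinine and adds: "The same procedure will be used for Day 90 Creatinine".
- **3.10.6** gives LOCF start days for Day 14 (from Day 10) and for Day 28 ("LOCF will be used for missing Day 28 creatinine starting from Day 7"). It gives none for Day 90.
- **4.2 and 8.3** list "Freedom from durable loss of renal function at Day 90" as a secondary endpoint. It is reported in Table 14.2.2.1 (mITT) and repeated in Tables 14.2.2.2 (AT) and 14.2.2.3 (PP). Protocol 5.3 places the same comparison among the exploratory objectives.

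The Day 90 creatinine is collected: it is Visit 11 in protocol 7.3, and the 3-month visit (numbered 10) in SAP Appendix 5.

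**The concern.** The formula is the only operational definition of Day 90 eGFR for this endpoint. A programmer who follows it will build the Day 90 renal criterion from a value drawn about eleven weeks earlier. Late recovery or late decline in creatinine would not reach the eGFR criterion. The Day 14 and Day 90 results would agree partly by construction and could be read as two separate findings pointing the same way. The protocol cannot settle the matter, because SAP section 1 says the SAP prevails where the two differ, and here the SAP disagrees with itself.

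**Working it through.** **Step 1. Compare the three formulas.**

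| SAP section | Creatinine named in the sentence | Creatinine in the formula |
|---|---|---|
| 3.10.3 Day 28 | Day 28 ("Day 28 eGFR will be determined by converting Day 28 creatinine to Day 28 eGFR using the following formula") | Day 28 |
| 3.10.4 Day 14 | Day 14 | Day 14 |
| 3.10.5 Day 90 | Day 90 | Day 14 |

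Only 3.10.5 is inconsistent. Its right-hand side is the same as that of 3.10.4, so as printed Day 90 eGFR = Day 14 eGFR for every patient.

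**Step 2. Express the criterion as a creatinine ratio.** The constant 175 and the age, sex and race factors cancel when both eGFRs use the same formula and the same age, so

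loss = 1 − (Cr at visit / base Cr)^−1.154.

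A 37% loss corresponds to a ratio of (1/0.63)^(1/1.154) = 1.492.

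Two reading choices are needed. The bracket printed in 3.10.5 divides only its second term; I read it as (base − value)/base. The base printed there is screening eGFR, whereas the endpoint definition in 4.1 says reference eGFR. I show both bases and apply the same eGFR formula to the reference creatinine. These two matters are separate from the present point.

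**Step 3. Put in values.** The creatinines (mg/dL) are illustrative assumptions, not figures from the documents.

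| Base Cr | Day 14 Cr | Day 90 Cr | Loss as printed (Day 14) | Loss with Day 90 Cr |
|---|---|---|---|---|
| Screening 1.1 | 1.2 | 2.2 | 1 − 1.091^−1.154 = 9.6%, pass | 1 − 2.0^−1.154 = 55.1%, fail |
| Screening 1.1 | 2.2 | 1.2 | 55.1%, fail | 9.6%, pass |
| Reference 1.0 | 2.0 | 1.1 | 1 − 2.0^−1.154 = 55.1%, fail | 1 − 1.1^−1.154 = 10.4%, pass |
| Reference 1.0 | 1.2 | 2.2 | 1 − 1.2^−1.154 = 19.0%, pass | 1 − 2.2^−1.154 = 59.7%, fail |
| Screening 2.0 | 2.0 | 1.1 | 0%, pass | 1 − 0.55^−1.154 = −99%, pass |

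Status can flip in either direction on either base. It does not flip for everyone. In the last row, a patient who entered with a doubled creatinine passes on the screening base whichever day is used. A screening value as low as 1.1 is possible because protocol 6.1 lets patients qualify on urine output alone.

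**Step 4. Check what else moves.** The endpoint also requires being alive and free of dialysis, and neither condition uses this formula. The Day 28 formula in 3.10.3 has the right day, so the primary test is not touched. No sample size or power figure depends on Day 90.

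**The case against.** The strongest reply is that this is a copying slip from 3.10.4 that nobody would follow. The sentence above the formula names the Day 90 creatinine, 5.11.2 imputes one, and the two sister sections each use their own day. That is probably right about intent. It means the documents do not establish that the endpoint will be computed from Day 14; they establish that a sentence and its formula conflict. The conflict still needs resolving, because the formula is what gets programmed and nothing in the SAP says which of the two governs.

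Two stronger readings are tempting and do not hold:

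- **That the whole Day 90 endpoint would repeat Day 14.** A reader might infer this, but only the eGFR component would. Deaths and dialysis after Day 14 still change the composite. Late renal information also appears elsewhere: Day 90 creatinine in Table 14.3.2.5, and Day 90 CKD incidence, with eGFR from the CKD-EPI equation, in Table 14.3.4.2.
- **That a share of the 120 patients would be misclassified.** The documents give no rate of crossing the 37% limit between Day 14 and Day 90. Nor can a rate be applied to all 120, since patients who are dead or on dialysis at Day 90 fail whatever their creatinine.

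It is also fair to say that the stakes are limited: the endpoint is outside the single primary hypothesis.

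**Conclusion.** The point holds as an internal contradiction in SAP 3.10.5, with a consequence conditional on programming the formula as printed. In that case the eGFR component at Day 90 equals Day 14 for every patient, and the 5.11.2 rule for Day 90 creatinine has no effect on it. The flips shown rest on illustrative creatinines and on reading the loss as (base − value)/base. They show that misclassification is possible in both directions, not how often it would occur. The effect is confined to an endpoint that is secondary in the SAP and exploratory in the protocol, and to the tables and subgroup summaries built on it. It should be corrected before unblinding, but it does not threaten the trial's main conclusion.

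**What to change.** 1. In the SAP 3.10.5 formula, replace Cr Day 14 with Cr Day 90, defined as the creatinine from protocol Visit 11 or, if missing, the value assigned under 5.11.2.
2. In 3.10.6, state the earliest day from which a value may be carried forward to Day 90, beside the start days for Days 14 and 28. Without it, the reference in 5.11.2 to the Day 28 procedure could be read as allowing a Day 7 value to stand for Day 90.
3. Program the Day 90 rows of Tables 14.2.2.1 to 14.2.2.3, and the subgroup versions, from that variable.

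The cost is one term and one line in the SAP, with a matching change in the derivation specification. No new data, visits or analyses are needed.
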